3.12.3 Pre-Discharge

Prior to hospital discharge the following data will be collected:

- Adverse Events
- Data regarding the use, changes in or discontinuation of anticoagulation, rate control and/or antiarrhythmic medications.
- Cardiac rhythm as determined by a 12-lead ECG
- Occurrence, date, indication and outcome of any cardioversion(s)
- At the investigator's discretion: a post-procedural mediastinal gadolinium-enhanced MRI
- Stroke/TIA assessments

- NIHSS score
- A neurologic examination will be performed and recorded if:
 - If the NIHSS score has increased by 2 or more points
 - If there is a clinical suspicion of stroke or TIA

3.12.4 30-Day Visit

Discharged subjects will return for an office visit 30 days (\pm 7 days) post-ablation treatment. (Any subject who continues to be hospitalized 30 days post-ablation will have their 30-Day Visit assessment performed in-hospital). The following data will be collected at the 30-Day Visit:

- Adverse Events
- Symptoms of recurrent arrhythmia
- Data regarding the use, changes in or discontinuation of anticoagulation, rate control and/or antiarrhythmic medications.
- Cardiac rhythm as determined by a 12-lead ECG at the time of the visit
- Cardioversions, ablations or hospital admissions since last visit
- Heart failure status as assessed by NYHA classification at the time of visit

3.12.5 75-Day Visit and Remapping Procedure

Patients undergoing protocol-specified remapping:

Subjects will undergo the protocol-stipulated remapping procedure at 75 ± 15 days post-Index Procedure as defined in **Section 3.11.2, 75-Day Remap Procedure**.

- A 3D electroanatomical remapping procedure will be performed to assess electrical isolation of the pulmonary veins. Any electrical gaps may be closed at the investigator's discretion using study devices, or if necessary, a commercially approved ablation device (which constitutes a Therapeutic Failure).
- For patients who received extra-PV ablation at index, including those receiving ablation of the CTI, the persistence of nonconductivity in targeted tissue will be evaluated with either pacing maneuvers or electroanatomical mapping.

Procedure-specific data will be collected as follows:

- Procedural times
- Lesion set data
- Device deficiencies and malfunctions

All subjects whether undergoing remapping or not:

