6.1 Primary Safety Endpoint

The primary safety endpoint for this study is the Composite Safety Endpoint (CSE) defined as the incidence of the following early-onset and late-onset serious adverse events (SAEs) which are device- or procedure-related, as adjudicated by the CEDMC and defined below in **Table 4. Composite Safety Endpoint Definitions**.

Early onset (within 30 days of an Index or Remap Procedure)

- Death
- Myocardial infarction (MI)
- Persistent diaphragmatic paralysis
- Stroke or transient ischemic attack (TIA)
- Peripheral or organ thromboembolism
- Pericarditis
- Cardiac tamponade / perforation
- Vascular access complications requiring intervention
- Heart block

Late onset (any time during follow-up through 12 months)

- Pulmonary vein (PV) stenosis (> 70% diameter reduction from baseline)
- Atrio-esophageal fistula

Table 4. Composite Safety Endpoint Definitions

Adverse Event	Description/Criteria
Death	Death
Myocardial infarction (MI)	Myocardial infarction will be demonstrated by any one of the following: 1) detection of ECG changes indicative of new ischemia (new ST-T wave changes or new LBB) that persist for more than 1 hour. 2) development of new pathological Q waves on an ECG 3) imaging evidence of new loss of viable myocardium or new regional wall motion abnormality
Persistent diaphragmatic paralysis	Diaphragmatic paralysis: Change from baseline diaphragmatic function as demonstrated radiographically by elevation of the diaphragm above the normal range but not due to a pulmonary process such as atelectasis. Permanent: not resolved by completion of study follow-up
Stroke or transient ischemic attack (TIA)	Stroke is an acute symptomatic episode of neurological dysfunction attributed to a vascular cause (ischemia or hemorrhage) in which symptoms last more than 24 hours, or if symptoms last less than 24 hours, a brain imaging study demonstrates infarction. Transient ischemic attack is a new focal neurological deficit with rapid symptom resolution always within 24 hours.

Adverse Event	Description/Criteria
Peripheral or organ thromboembolism	Formation in a blood vessel of a clot (thrombus) that results from the breaking loose of all or part of an existing thrombus, which is then carried by the blood to lodge in/occlude a more distal vascular site.

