2.4.8.2. Secondary Safety Analysis

The proportion of subjects reporting one or more SAEs for each follow-up interval. The intervals will include the period from:

- The Primary Safety Endpoint assessed at 7 rather than 30 days
- The proportion of subjects with a device- or procedure-related SAE
- The proportion of subjects with stroke or TIA
- The proportion of subjects requiring cardioversion
- The proportion of subjects requiring an arrhythmia-related hospitalization.

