2.5. Derived Criteria Calculation

If at least one of the items needed to calculate a derived criteria is missing, then the corresponding derived criteria will be considered as missing.

Patient Disposition:

- Derived criteria “Enrolled population” will be analysed as:
IF the date of patient consent is filled in **Patient eligibility form (IE)** **THEN** “Enrolled population” = ‘Yes’
ELSE “Enrolled population” = ‘No’.
- Derived criteria “ITT population” will be defined as follows:
IF “Enrolled population” = ‘Yes’ in **Patient eligibility form (IE)** and the date of the Procedure is filled in **Procedural data form (PR)** **THEN** “ITT population” = ‘Yes’
ELSE “ITT population” = ‘No’.
- Derived criteria “Per Protocol population PP” will be defined as follows:
IF “ITT population” = ‘Yes’ **AND** Device Deficiency Number is not filled **AND** Serial # is not filled in **Device Deficiency DD Form** **THEN** Per Protocol population = ‘Yes’
ELSE Per Protocol population = ‘No’.
- Derived criteria “Time of patient follow-up” will be calculated as:
Date of study exit/withdrawal (*) in **Patient eligibility form (IE)** – date of procedure in **Procedural data form (PR)**
*if the patient is still in the study, the last visit date will be used instead of the exit/ withdrawal one.
- Derived criteria “COVID status” will be calculated as:
IF “Related to COVID-19 situation” =1 **OR** the term “COVID” exist in “reason for deviation” **AND** date of deviation is filled in **Protocol deviation form (PD)**, **THEN** CLASS=“ COVID-19”
ELSE IF date of deviation is filled **THEN** CLASS= “NOT COVID-19”.

Baseline Patient Characteristics:

- Derived criteria “Time from first AF diagnosis until consent date (months)” will be defined as follows:
Informed consent date – date of first documented AF diagnosis in **AF history form (AH)**.
- Derived criteria “Time between the most recent AF episode and the enrollment (months)” will be defined as follows:
Informed consent date – date of most recent AF episode in **AF history form (AH)**.
- Derived criteria “Permanent pacemaker or ICD” will be defined as follows:
IF Pacemaker, Implantable Cardioverter Defibrillator or Cardiac Resynchronization therapy device= ‘Yes’ in **Patient eligibility Form (IE)** **THEN** Permanent pacemaker or ICD=‘Yes’

CONFIDENTIEL / CONFIDENTIAL

Toute reproduction ou distribution, totale ou partielle, de ce document, sans autorisation préalable de ICON PLC est interdite.

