IF (30≤ (EVENT DATE-PROCEDURE DATE IN **PROCEDURAL DATA FORM (PR)**) **OR** (30≤ (EVENT DATE-≤REMAPPING DATE IN **FOLLOW-UP 3D ELECTROANATOMICAL MAPPING FORM (RM)**) **AND** PRIMARY SAFETY ENDPOINT EVENT CRITERIA=' Death' **THEN** DEATH='Yes'
ELSE DEATH='No'

- Derived criteria "Myocardial infarction" will be defined as follows:

IF (30≤ (EVENT DATE-PROCEDURE DATE IN **PROCEDURAL DATA FORM (PR)**) **OR** (30≤ (EVENT DATE-REMAPPING DATE IN **FOLLOW-UP 3D ELECTROANATOMICAL MAPPING FORM (RM)**) **AND** PRIMARY SAFETY ENDPOINT EVENT CRITERIA=' Myocardial infarction' **THEN** Myocardial infarction='Yes'.

ELSE Myocardial infarction ='No'.

- Derived criteria "PV Stenosis" will be defined as follows:

IF (0≤ (EVENT DATE-PROCEDURE DATE IN **PROCEDURAL DATA FORM (PR)**) ≤360 **AND** PRIMARY SAFETY ENDPOINT EVENT CRITERIA=' PV Stenosis' **THEN** PV Stenosis ='Yes'.
ELSE PV Stenosis ='No'.

- Derived criteria "Diaphragmatic Paralysis" will be defined as follows:

IF (30≤ (EVENT DATE-PROCEDURE DATE IN **PROCEDURAL DATA FORM (PR)**) **OR** (30≤ (EVENT DATE-REMAPPING DATE IN **FOLLOW-UP 3D ELECTROANATOMICAL MAPPING FORM (RM)**) **AND** PRIMARY SAFETY ENDPOINT EVENT CRITERIA=' Diaphragmatic Paralysis' **THEN** Diaphragmatic Paralysis ='Yes'.
ELSE Diaphragmatic Paralysis ='No'.

- Derived criteria "AE fistula" will be defined as follows:

IF (0≤ (EVENT DATE-PROCEDURE DATE IN **PROCEDURAL DATA FORM (PR)**) ≤360 **AND** PRIMARY SAFETY ENDPOINT EVENT CRITERIA=' AE fistula' **THEN** AE fistula ='Yes'.
ELSE AE fistula ='No'.

- Derived criteria "TIA" will be defined as follows:

IF (30≤ (EVENT DATE-PROCEDURE DATE IN **PROCEDURAL DATA FORM (PR)**) **OR** (30≤ (EVENT DATE-REMAPPING DATE IN **FOLLOW-UP 3D ELECTROANATOMICAL MAPPING FORM (RM)**) **AND** PRIMARY SAFETY ENDPOINT EVENT CRITERIA=' TIA' **THEN** TIA=Yes.
ELSE TIA='No'.

- Derived criteria "CVA" will be defined as follows:

CONFIDENTIEL / CONFIDENTIAL

Toute reproduction ou distribution, totale ou partielle, de ce document, sans autorisation préalable de ICON PLC est interdite.
Reproduction and distribution of this document, in whole or in part, is strictly forbidden without prior authorization from ICON PLC.

	STATISTICAL ANALYSIS PLAN	FARAPULSE PersAFOne SAP V1.0 PERSAFONE Page 27 /49
---	----------------------------------	--

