IF (7≤ (EVENT DATE-PROCEDURE DATE IN PROCEDURAL DATA FORM (PR)) **OR** (7≤ (EVENT DATE-REMAPPING DATE IN FOLLOW-UP 3D ELECTROANATOMICAL MAPPING FORM (RM)) **AND** PRIMARY SAFETY ENDPOINT EVENT CRITERIA=’ Death’ **THEN** DEATH=’Yes’
ELSE DEATH=’No’
- Derived criteria “Myocardial infarction 7 days” will be defined as follows:
IF (7≤ (EVENT DATE-PROCEDURE DATE IN PROCEDURAL DATA FORM (PR)) **OR** (7≤ (EVENT DATE-REMAPPING DATE IN FOLLOW-UP 3D ELECTROANATOMICAL MAPPING FORM (RM)) **AND** PRIMARY SAFETY ENDPOINT EVENT CRITERIA=’ Myocardial infarction’ **THEN** Myocardial infarction=’Yes’.
ELSE Myocardial infarction = ‘No’.
- Derived criteria “Diaphragmatic Paralysis 7 days” will be defined as follows:

CONFIDENTIEL / CONFIDENTIAL

Toute reproduction ou distribution, totale ou partielle, de ce document, sans autorisation préalable de ICON PLC est interdite.
Reproduction and distribution of this document, in whole or in part, is strictly forbidden without prior authorization from ICON PLC.

	STATISTICAL ANALYSIS PLAN	FARAPULSE PersAFOne SAP V1.0 PERSAFONE Page 29 /49
---	----------------------------------	--

IF (7≤ (EVENT DATE-PROCEDURE DATE IN PROCEDURAL DATA FORM (PR)) **OR** (7≤ (EVENT DATE-REMAPPING DATE IN FOLLOW-UP 3D ELECTROANATOMICAL MAPPING FORM (RM)) **AND** PRIMARY SAFETY ENDPOINT EVENT CRITERIA=' Diaphragmatic Paralysis' **THEN** Diaphragmatic Paralysis ='Yes'.
ELSE Diaphragmatic Paralysis ='No'.

- Derived criteria "TIA 7 days" will be defined as follows:

IF (7≤ (EVENT DATE-PROCEDURE DATE IN PROCEDURAL DATA FORM (PR)) **OR** (7≤ (EVENT DATE-REMAPPING DATE IN FOLLOW-UP 3D ELECTROANATOMICAL MAPPING FORM (RM)) **AND** PRIMARY SAFETY ENDPOINT EVENT CRITERIA=' TIA' **THEN** TIA='Yes'.
ELSE TIA='No'.

- Derived criteria "CVA 7 days" will be defined as follows:

IF (7≤ (EVENT DATE-PROCEDURE DATE IN PROCEDURAL DATA FORM (PR)) **OR** (7≤ (EVENT DATE-REMAPPING DATE IN FOLLOW-UP 3D ELECTROANATOMICAL MAPPING FORM (RM)) **AND** PRIMARY SAFETY ENDPOINT EVENT CRITERIA=' CVA' **THEN** CVA='Yes'.
ELSE CVA='No'.

- Derived criteria "Major pericarditis 7 days" will be defined as follows:

IF (7≤ (EVENT DATE-PROCEDURE DATE IN PROCEDURAL DATA FORM (PR)) **OR** (7≤ (EVENT DATE-REMAPPING DATE IN FOLLOW-UP 3D ELECTROANATOMICAL MAPPING FORM (RM)) **AND** PRIMARY SAFETY ENDPOINT EVENT CRITERIA=' Major pericarditis' **THEN** Major pericarditis = 'Yes'.
ELSE Major pericarditis = 'No'.

- Derived criteria "Tamponade/Perforation 7 days" will be defined as follows:

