- Derived criteria “Stroke after index procedure” will be defined as follows:
IF Event name='STROKE' in **Adverse event form** **AND** Event start date ≥ Procedure date in **Procedural data Form (PR)** **THEN** STROKE='Yes'
ELSE STROKE='No'
- Derived criteria “Transient Ischemic Attack (TIA) after index procedure” will be defined as follows:
IF Event name=' Transient Ischemic Attack' in **Adverse event form** **AND** Event start date ≥ Procedure date in **Procedural data Form (PR)** **THEN** TIA='Yes'
ELSE TIA='No'
- Derived criteria “Stroke after Remap procedure” will be defined as follows:
IF Event name='STROKE' in **Adverse event form** **AND** Event start date ≥ Remap date IN **FOLLOW-UP 3D ELECTROANATOMICAL MAPPING FORM (RM)** **THEN** STROKE='Yes'
ELSE STROKE='No'
- Derived criteria “Transient Ischemic Attack (TIA) after Remap procedure” will be defined as follows:
IF Event name=' Transient Ischemic Attack' in **Adverse event form** **AND** Event start date ≥ Remap date in **FOLLOW-UP 3D ELECTROANATOMICAL MAPPING FORM (RM)** **THEN** TIA='Yes'
ELSE TIA='No'
- Derived criteria “Arrhythmia-related (AF, AFL, AT) hospitalization” will be defined as follows:
IF Arrhythmia-related (AF, AFL, AT) hospitalization ='Yes' in **MDT excel file** **THEN** Arrhythmia-related (AF, AFL, AT) hospitalization ='Yes'
ELSE IF Arrhythmia-related (AF, AFL, AT) hospitalization ='No' in **MDT excel file** **THEN** Arrhythmia-related (AF, AFL, AT) hospitalization ='No'
- Derived criteria “Death” will be defined as follows:
IF SAE: Death='Yes' in **Adverse event form** **OR** Reason ='Patient death' in **study exit form** **THEN** Death='Yes'
ELSE Death='No'

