4.1.8. Table 8. Primary Safety Endpoint –Composite Safety Endpoint (CSE)

	ITT Population N = XX	
	n/N (%)	[95% CI]
Early and Late Onset Composite Safety Endpoint	XX/XX (XX.X%)	[XX% - XX%]
Total Early (within 30 days of Index or Remap Procedure)	XX/XX (XX.X%)	[XX% - XX%]
Death	XX/XX (XX.X%)	[XX% - XX%]
Myocardial infarction (MI)	XX/XX (XX.X%)	[XX% - XX%]
Persistent diaphragmatic paralysis	XX/XX	[XX% - XX%]

CONFIDENTIEL / CONFIDENTIAL

Toute reproduction ou distribution, totale ou partielle, de ce document, sans autorisation préalable de ICON PLC est interdite.
Reproduction and distribution of this document, in whole or in part, is strictly forbidden without prior authorization from ICON PLC.

Stroke	(XX.X%)	
Transient ischemic attack (TIA)	XX/XX (XX.X%)	[XX% - XX%]
Peripheral or organ thromboembolism	XX/XX (XX.X%)	[XX% - XX%]
Pericarditis	XX/XX (XX.X%)	[XX% - XX%]
Cardiac tamponade / perforation	XX/XX (XX.X%)	[XX% - XX%]
Vascular access complications requiring intervention	XX/XX (XX.X%)	[XX% - XX%]
Heart block	XX/XX (XX.X%)	[XX% - XX%]
Total Late (any time during follow-up through 12 months)	XX/XX (XX.X%)	[XX% - XX%]
Pulmonary vein (PV) stenosis (> 70% diameter reduction from baseline)	XX/XX (XX.X%)	[XX% - XX%]
Atrio-esophageal fistula	XX/XX (XX.X%)	[XX% - XX%]

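### SAP 2.5 reverses the early-onset window of the primary safety endpoint: index complications on days 0–29 score No, and the 7-day version loses days 0–6

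*SAP*

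**What the plan says.** The endpoint definition is the same wherever it appears in prose. Protocol 6.1 heads the first group of components "Early onset (within 30 days of an Index or Remap Procedure", SAP 2.4.8.1 repeats it, and the row label in SAP Table 8 reads "Total Early (within 30 days of Index or Remap Procedure". The secondary version in SAP 2.4.8.2 is "The Primary Safety Endpoint assessed at 7 rather than 30 days".

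SAP 2.5 turns this into code. Each early component is Yes if "30≤ (EVENT DATE-PROCEDURE DATE IN" the procedural form holds, or if the same test against the remapping date holds, and the adjudicated event criterion matches. Otherwise it is No. The seven-day components use "7≤ (EVENT DATE-PROCEDURE DATE IN PROCEDURAL DATA FORM (PR" in the same way. The two late-onset components (PV stenosis and atrio-esophageal fistula) are written as a difference from 0 to 360 days after the procedure.

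SAP 2.5 also has a general rule: "If at least one of the items needed to calculate a derived criteria is missing", the derived criterion is itself missing.

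**The concern.** A test that 30 is less than or equal to the elapsed days selects events from day 30 onward. The stated window is day 0 to day 30. The two share only day 30 of the index window.

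The days lost are those the primary safety endpoint exists to measure: complications of the index ablation. Because the date test is joined by AND to the adjudicated criterion, correct adjudication cannot bring a lost event back. The rates at risk are those in SAP Table 8 (primary safety) and the 7-day rows of SAP Table 12.

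The rules also conflict with two other parts of the plan:

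- Protocol Table 4 defines tamponade as arising during, or within 30 days of, the index ablation. A tamponade meeting that definition could pass the SAP rule only on day 30.
- The stroke item among the secondary safety derivations uses "Event start date ≥ Procedure date in" the procedural form. A stroke on day 2 would therefore be Yes in Table 12 and No in the Table 8 composite.

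**Working it through.** The plan has no hypothesis test and no expected rate, so there is no stated figure to reproduce. The check evaluates the rules day by day.

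**Inputs.** Let d be days from index to event and R the remap day. R is 75 ± 15, so 60 to 90 (Protocol 3.12.5). Follow-up is taken as days 0–365. N is up to 40 (Protocol 3.7); SAP Tables 5 and 19 print N = 25.

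**Extent.** SAP 2.5 derives 12 early components: death, MI, diaphragmatic paralysis, TIA, CVA, major pericarditis, tamponade/perforation, pneumothorax, heart block, pulmonary edema, hospitalization and vascular access. The same 12 recur in the 7-day set, making 24 rules with the reversed test. The 0-to-360 form and the ≥ sign print correctly in the same section, so a text-extraction fault is unlikely.

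**30-day rule, R = 60, 75 or 90.**
- Definition: days 0–30 and R to R+30, which is 31 + 31 = 62 days.
- SAP rule: d ≥ 30 or d − R ≥ 30. The second clause implies the first, so Yes means days 30–365: 365 − 30 + 1 = 336 days.
- Overlap: day 30 plus the 31 remap days = 32.
- Missed: 62 − 32 = 30 (days 0–29). Admitted outside both windows: 336 − 32 = 304.

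**7-day rule.**
- Definition: 8 + 8 = 16 days. SAP rule: 365 − 7 + 1 = 359. Overlap: 1 + 8 = 9.
- Missed: 16 − 9 = 7 (days 0–6). Admitted: 359 − 9 = 350.

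Events within 30 (or 7) days after the remap are still counted, because they lie at least 30 (or 7) days after index.

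**No remap.** Protocol 3.12.5 provides for this with "All subjects whether undergoing remapping or not". If the remap clause is treated as false, the definition covers 31 days and the rule 336, with only day 30 in common. If the missing-item rule is applied instead, the component becomes missing. On both readings an event on days 0–29 is not counted.

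**Brackets.** Each rule opens six and closes four. If AND is evaluated before OR, any event 30 or more days after index scores Yes for every early component, whatever its type. Days 0–29 are lost on either reading.

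**Reversing the sign alone.** With d ≤ 30 or d − R ≤ 30 and no lower bound, events before the remap give a negative difference and pass. Yes then covers days 0 to R+30, or R + 31 days. The excess is R + 31 − 62 = R − 31: 29, 44 or 59 days. For the 7-day rule it is R + 8 − 16 = R − 8: 52, 67 or 82 days.

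**Effect on the reported rate**, assuming the true events are index events before day 30 (exact intervals; Agresti-Coull at 0%, as SAP 2.1.4 sets):

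| True | Reported under SAP 2.5 |
|---|---|
| 1/40 = 2.5% (0.1–13.2%) | 0/40 (0–10.4%) |
| 2/40 = 5.0% (0.6–16.9%) | 0/40 (0–10.4%) |
| 1/25 = 4.0% (0.1–20.4%) | 0/25 (0–15.8%) |

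**Late-onset cut.** The 12-month visit is 365 ± 30 days. A limit of 360 drops days 361–365 for a subject followed to day 365, and up to day 395 for one seen at the end of the window.

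**The case against.** The best reply is that this is a drafting slip. The SAP states the window correctly in 2.4.8.1 and in the Table 8 label, and SAP 2.5 is informal pseudocode with other visible errors, including a stray ≤ inside the Death rule. A careful programmer might see the conflict, and nothing shows that the rule was run as written. That is fair as to cause. But the reversed form appears in 24 rules, SAP 2.5 is the part meant to be programmed, and the documents do not say which section prevails.

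Several limits on the consequences stand:

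- The 304 and 350 admitted days are calendar days up to an assumed day 365, not misclassified events. If the adjudicated criterion field already enforces timing, over-counting is nil. The documents do not say.
- The missing-item rule, read literally, would also make event-free subjects missing for want of an event date, despite the explicit No. That reading is doubtful, and the point calls only for clarification.
- A subject who exits by day 360 loses nothing to the late-onset cut, and PV imaging is scheduled only at baseline and 75 days. That point is minor.
- The study is descriptive. Lost events still appear in SAP Table 15 and Listing 17, and the CEDMC reviews case summaries and source documents, so safety oversight does not depend on this code.

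None of this corrects the rates in Tables 8 and 12.

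**Conclusion.** The concern holds. As written, SAP 2.5 contradicts Protocol 6.1 and the SAP's own definition, and it must be corrected before the primary safety endpoint is produced.

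The loss of index days 0–29 (0–6 in the 7-day version) is certain if the rules are programmed literally, whatever the remap day and however the brackets are read. Over-counting of later events is conditional on the adjudicated field not enforcing timing. Complications within 30 days of the remap are not lost.

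The rate examples are hypothetical, since the documents give no expected event rate. Early index events are plausible: Protocol 1.3.1 reports a tamponade at the end of the Index Procedure in the sponsor's earlier 40-patient study, and such an event would score No here.

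**What to change.** Rewrite every early-onset component in SAP 2.5 as:

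`[(0 ≤ event date − index date ≤ 30) OR (remap done AND 0 ≤ event date − remap date ≤ 30)] AND event criterion = X`

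- Keep the outer bracket around the OR.
- State that the remap clause is false, not missing, when no remap was done.
- Use 7 in place of 30 for the 7-day endpoint.
- For PV stenosis and fistula, replace the 360-day limit with the end of 12-month follow-up, and define that day.

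Make the change before programming. If Tables 8 and 12 already exist, check how they were coded and rerun them as needed. The cost is SAP text and program code, with no new data and no protocol amendment.

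This does not settle the component list, which needs its own correction: thromboembolism has no derivation, while pneumothorax, pulmonary edema and hospitalization enter the SAP composite without being in the protocol definition.

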- Heart failure status as assessed by NYHA classification at the time of visit

3.12.7 12-Month Visit

Subjects will return for an office visit 12 months (365 days \pm 30 days) following the Index Procedure. At a minimum, the following data will be collected at the 12-Month Visit:

- Adverse Events

- Symptoms of recurrent arrhythmia
- If either the post-Index Procedure or post-75-Day Remap Procedure fluoroscopies indicated diminished phrenic nerve response, and resolution has not been previously demonstrated, a repeat fluoroscopic examination. Females of childbearing potential undergoing this examination will also receive a pregnancy test prior.
- Data regarding the use, changes in or discontinuation of anticoagulation, rate control and/or antiarrhythmic medications.
- Cardiac rhythm as determined by a 12-lead ECG at the time of the visit
- Arrhythmia assessment (See **Section 3.11.4, Arrhythmia Core Lab**).
 - A 24-hour continuous ECG monitor will be provided to the subject.
 - Instructions for returning the Event Monitor will be provided
- Cardioversions, ablations or hospital admissions since last visit
- Heart failure status as assessed by NYHA classification at the time of visit

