1.3.3. Study Assessments

The following flowchart applies to the study:

Assessment	Baseline	Procedure	Pre-Discharge	30-Days Post-Procedure (± 7 days)	75-Days (± 15 days)	6-Month (180 ± 30 days)	12-Month (365 ± 30 days)	Unscheduled
Medical History, CHA ₂ DS ₂ -VASc	X							
AFD and Anticoagulant Medications	X		X	X	X	X	X	X
Symptoms of recurrent arrhythmia				X	X	X	X	X
History of cardioversions, ablations, hospital admissions since last visit			X	X	X	X	X	X
Pregnancy test (for females of childbearing potential)	X	X			X			
12-lead ECG	X		X	X	X	X	X	X
24-Hour Continuous ECG Monitor (e.g., Holter)						X	X	
Cardiac CT/MRI for LA and PV dimensions	X				X			
Mediastinal MRI			X ¹					
TEE or other imaging modality (to exclude left atrial thrombus)	X							
Electroanatomical Mapping		X			X			
Event Monitor readiness/compliance					X	X	X	X
NIHSS	X		X					
Neurologic exam			X ²					
NYHA Classification	X		X	X	X	X	X	X
Fluoroscopic Examination of Diaphragm		X			X if remapped, X ³ if not	X ³	X ³	
Adverse Events		X	X	X	X	X	X	X

¹ At investigator's discretion

² If NIHSS score has increased by 2 or more points or if clinical suspicion of stroke/TIA

³ If the Index Procedure or Remap Procedure study indicated decreased phrenic nerve function and resolution has not yet been demonstrated.

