2.1.4. Inferential Analysis

- Confidence intervals:

When applicable, bilateral asymptotic or exact confidence intervals for binomial distributions will be calculated at the 95% level.

For categorical variables, if pertinent, the 95% asymptotic confidence interval will be calculated if theoretical assumptions are verified. If this is not the case, and the corresponding proportion is 0% or 100%, then the Agresti-Coull confidence interval will be calculated instead. In all other cases, the exact confidence interval will be calculated.

- Survival analysis:

Time-to-event variables will be described over time by survival curves as per the Kaplan-Meier method together with the associated estimators, considering the upper window of the corresponding visits. The survival rate will be presented at each time point (30 days, 90 days, 180 days, 365 days) and overall.

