2.4.8.1. Primary Safety Analysis

The primary safety endpoint for this study is the Composite Safety Endpoint (CSE) defined as the incidence of the following early-onset and late-onset serious adverse events (SAEs) which are device- or procedure-related, as adjudicated by the CEDMC.

CONFIDENTIEL / CONFIDENTIAL

Toute reproduction ou distribution, totale ou partielle, de ce document, sans autorisation préalable de ICON PLC est interdite.
Reproduction and distribution of this document, in whole or in part, is strictly forbidden without prior authorization from ICON PLC.

STATISTICAL ANALYSIS PLAN

FARAPULSE PersAFOne SAP V1.0

PERSAFONE

Page 18 /49

Composite Safety Endpoint Definitions:

Early onset (within 30 days of an Index or Remap Procedure)

- Death
- Myocardial infarction (MI)
- Persistent diaphragmatic paralysis
- Stroke or transient ischemic attack (TIA)
- Peripheral or organ thromboembolism
- Pericarditis
- Cardiac tamponade / perforation
- Vascular access complications requiring intervention
- Heart block

Late onset (any time during follow-up through 12 months):

- Pulmonary vein (PV) stenosis (> 70% diameter reduction from baseline)
- Atrio-esophageal fistula

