ELSE New or Prolonged Hospitalization, excl. AF/AFL ='No'

CONFIDENTIEL / CONFIDENTIAL

Toute reproduction ou distribution, totale ou partielle, de ce document, sans autorisation préalable de ICON PLC est interdite.
Reproduction and distribution of this document, in whole or in part, is strictly forbidden without prior authorization from ICON PLC.

	STATISTICAL ANALYSIS PLAN	FARAPULSE PersAFOne SAP V1.0 PERSAFONE Page 28 /49
---	----------------------------------	--

- Derived criteria “Vascular Access Complication” will be defined as follows:
IF (30≤ (EVENT DATE-PROCEDURE DATE IN PROCEDURAL DATA FORM (PR)) **OR** (30≤ (EVENT DATE-REMAPPING DATE IN FOLLOW-UP 3D ELECTROANATOMICAL MAPPING FORM (RM)) **AND** PRIMARY SAFETY ENDPOINT EVENT CRITERIA=’ Vascular Access Complication’ **THEN** Vascular Access Complication =’Yes’
ELSE Vascular Access Complication =’No’
- Derived criteria “Total Early and Late Onset Composite Safety Endpoint” will be defined as follows:
IF Death=Yes **OR** Myocardial infarction =Yes **OR** PV Stenosis =Yes **OR** Diaphragmatic Paralysis =Yes **OR** AE fistula =Yes **OR** TIA =Yes **OR** CVA=Yes **OR** Major pericarditis =Yes **OR** Tamponade/Perforation =Yes **OR** Pneumothorax =Yes **OR** Heart Block =Yes **OR** Pulmonary Edema =Yes **OR** New or Prolonged Hospitalization, excl. AF/AFL =Yes **OR** Vascular Access Complication =Yes **THEN** Total Early and Late Onset Composite Safety Endpoint =’Yes’
ELSE Total Early and Late Onset Composite Safety Endpoint =’No’
- Derived criteria “Total Early Onset Composite Safety Endpoint” will be defined as follows:
IF Death=Yes **OR** Myocardial infarction =Yes **OR** Diaphragmatic Paralysis =Yes **OR** TIA =Yes **OR** CVA=Yes **OR** Major pericarditis =Yes **OR** Tamponade/Perforation =Yes **OR** Heart Block =Yes **OR** New or Prolonged Hospitalization, excl. AF/AFL =Yes **OR** Vascular Access Complication =Yes **THEN** Total Early Onset Composite Safety Endpoint=’Yes’
ELSE Total Early Onset Composite Safety Endpoint=’No’
- Derived criteria “Total Late (any time during follow-up through 12 months)” will be defined as follows:
IF PV Stenosis =Yes **OR** AE fistula =Yes **THEN** Total Late (any time during follow-up through 12 months) =’Yes’
ELSE Total Late (any time during follow-up through 12 months) =’No’.

Secondary Safety endpoint

- Derived criteria “Death 7 days” will be defined as follows:

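### The SAP counts late-onset safety events only to day 360, which is short of the 12-month endpoint and of the day-365 ± 30 final visit

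*SAP*

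**What the plan says.** Protocol 6.1 and SAP 2.4.8.1 give the two late-onset components of the Composite Safety Endpoint, pulmonary vein (PV) stenosis and atrio-esophageal fistula, the same time frame. The SAP words it as "Late onset (any time during follow-up through 12 months". The derived late-onset total in SAP 2.5 repeats it ("Total Late (any time during follow-up through 12 months"), as do the row labels of Tables 8 and 12.

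Both documents place the final visit at day 365 ± 30. Protocol 3.12.7 says "Subjects will return for an office visit 12 months (365 days \pm 30 days) following the Index Procedure", and the SAP's assessment flowchart (1.3.3) heads the column "12-Month (365 ± 30 days". Protocol 3.10.1 has subjects exit once they have completed that visit.

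The derivations in SAP 2.5 are narrower. Both take event date minus index procedure date and require a value from 0 to 360:

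- PV stenosis: "≤360 AND PRIMARY SAFETY ENDPOINT EVENT CRITERIA=' PV Stenosis' THEN PV Stenosis ='Yes"
- Fistula: "≤360 AND PRIMARY SAFETY ENDPOINT EVENT CRITERIA=' AE fistula' THEN AE fistula ='Yes"

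Everything else goes to the default branch, for example "ELSE PV Stenosis ='No". Neither document explains the figure 360 or adds a rule for later days.

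**The concern.** The program for the primary safety endpoint covers a shorter period than the endpoint it implements. The day limit is joined by AND to the committee's endpoint classification, so an adjudicated event that is one day too late is overridden and recorded as no event. Although SAP 2.1.2 gives precedence to committee-reviewed data, here a date limit overrules the committee's classification.

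The study is descriptive with no hypothesis test (Protocol 5.3, SAP 2.2), so the reported counts and intervals are the result. Whether Table 8 shows zero or one late-onset event is what a reader will take away. Taken alone, the cut-off can only remove events, so any error favours the device. Table 8 would also carry a label that its contents do not meet.

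**Working it through.** **Inputs.** The programmed limit is C = 360 days (SAP 2.5, both rules). The 12-month visit is day 365 ± 30 (Protocol 3.12.7, SAP 1.3.3). Planned enrolment is up to 40 (Protocol 3.7). N = 25 stands in the shells of SAP Tables 5 and 19.

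**Where 360 might come from.** 12 × 30 = 360, but neither document adopts a 30-day month for the year. 12 × 30.4375 = 365.25, and SAP 2.1.4 uses 365 days as its 12-month time point. Only the unstated convention gives 360.

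**Shortfall.**

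- Against the target day: 365 − 360 = 5 days.
- Against the end of the window: 365 + 30 = 395, and 395 − 360 = 35 days (361 to 395).

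**The rule applied to an event dated day 365.** The test 0 ≤ 365 ≤ 360 is false, so the component is 'No'. The late-onset total is 'No' unless the other late component is met. The overall composite is 'No' unless another component is met.

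**Alternative limits.** The window, days 335 to 395, has 395 − 335 + 1 = 61 days.

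| Limit | Event dates in the window that count | Event dates in the window scored 'No' |
|---|---|---|
| 360 (as written) | 335–360 (26 days) | 361–395 (35 days) |
| 365 | 335–365 (31 days) | 366–395 (30 days) |
| 395, or visit/exit date | every date up to the subject's exit | none |

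**Effect of one dropped event,** assuming that it is the only composite event. The exact interval is used for one event. For zero events the SAP 2.1.4 rule leads to Agresti-Coull, with the lower limit cut at 0.

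- N = 40: 1/40 = 2.5% (95% CI 0.06% to 13.16%) becomes 0/40 = 0% (0% to 10.44%).
- N = 25: 1/25 = 4.0% (0.10% to 20.35%) becomes 0/25 = 0% (0% to 15.76%).

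**The case against.** The mismatch itself is hard to defend, but its reach is limited. Several stronger readings should be resisted.

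- **Share of events lost.** Since 35 of the 61 allowed visit days (57%) lie beyond day 360, a reader might infer that more than half of late events are lost. The rule tests the event date, not the visit date: an event found at a day-370 visit but dated day 350 still counts. If event dates were spread evenly over days 0 to 395 (an assumption; the documents give no distribution), 35/396 = 8.8% would fall after the cut-off. Over days 0 to 365 it would be 5/366 = 1.4%.
- **PV stenosis found at the final visit.** Cardiac CT/MRI after baseline is scheduled only at 75 days (Protocol Table 3). A stenosis first dated around month 12 would normally need unscheduled imaging. A fistula diagnosis does not depend on that scan.
- **Only contact after month 6.** A reader might infer that these events could surface only at the 12-month visit. It is the only scheduled visit after month 6, but unscheduled visits collect adverse events (Protocol 3.12.8) and serious events must be notified within 24 hours (Protocol 7.8).
- **Visible only in a listing.** The device- and procedure-related SAE rules in SAP 2.5 have no upper date limit and feed Table 12, and Table 15 tabulates all SAEs. A dropped event could still appear in both. The loss is from the late-onset total and the primary composite.
- **Breach of the survival rule.** SAP 2.1.4 speaks of "considering the upper window of the corresponding visits", but for Kaplan-Meier variables. The composite is a proportion, so that rule is only indirect support.
- **Day 395 as the only reading.** Protocol 3.9 speaks of follow-up for up to 12 months, so a fixed limit of day 365 can be argued. The gap is then five days, and 360 is still wrong.

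All of this lowers the likely number of affected events. None of it explains 360 or makes the rule match the endpoint.

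**Conclusion.** The point stands as an error in two derivation rules of the primary safety endpoint. The programmed window ends 5 days before the target 12-month day and 35 days before the last permitted visit day. An adjudicated PV stenosis or fistula dated on days 361 to 395 is scored as absent.

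The expected effect is small, probably no event at all. At worst, under the stated assumption of a single composite event, it is the difference between 2.5% and 0% with 40 subjects. No success criterion depends on it. The direction is known only for this cut-off taken alone; how the early-onset date conditions in the same section are written is a separate matter.

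The 35-day figure rests on reading the endpoint as running to the end of each subject's follow-up, which the exit rule in Protocol 3.10.1 supports. On the narrowest reading, day 365, the 5-day gap remains. SAP section 1 cites Revision C of the protocol and the protocol at hand is Revision E, but this does not explain the mismatch, because the SAP's own flowchart uses 365 ± 30.

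**What to change.** In SAP 2.5, in both the PV Stenosis and the AE fistula rules, replace the upper limit of 360 with a condition that the event date is on or before the subject's 12-month visit or study-exit date, with day 395 (365 + 30) as the latest allowed. The late-onset rows of Tables 8 and 12 would then match their labels.

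If the sponsor intends 12 months as a fixed day, the limit should be at least 365, and the SAP should state it and carry it into the table labels. Events at in-window visits on days 366 to 395 would then be left out by declared choice.

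The cost is one condition in two rules and a minor SAP revision. No new data, visits or protocol amendment are needed. As far as this cut-off is concerned, the late-onset rate can only stay the same or rise.
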